ⁿ Full pulmonary function test (PFT) results will include forced expiratory volume in 1 second (FEV1), forced vital capacity (FVC), FVC % predicted (NHANES III reference values), FEV1/FVC ratio, peak expiratory flow rate (PEFR) or forced expiratory flow at maximum effort (FEF_{max}), total lung capacity, residual volume, diffusing capacity of the lungs for carbon monoxide (DLCO; uncorrected for Hb), DLCO: % predicted and DLCO/alveolar volume.

^o High-resolution computed tomography (HRCT) should be performed within 28 days of Day -1. Both CXR and HRCT should be evaluated side by side by investigator/radiologist/central reader for determining if the condition is improving, stable, or deteriorating based on a 5-point Likert score: much worse; worse; unchanged; better; much better. The CXR will also include Scadding scoring ([Attachment 11](#)).

^p The Six Minute Walk Test (6MWT) would be performed according to the ATS protocol ([Attachment 12](#)). Reasons for not performing the 6MWT will be captured in eCRF.

^q Subjects (and/or caregivers) will be trained on SC injections using the training tools provided separately. Additional training may be provided during Visit 2 before randomization occurs. SC injections training may be forgone if either the subject or caregiver is a medically trained professional.

^r The importance of adhering to treatment will be encouraged at every visit. At Visit 8, IMP will only be dispensed for subjects participating in the optional Open-label Extension Phase.

^s Dosing will begin after Visit 2 procedures are completed and subject is randomized. The first dose of study drug for all subjects will be administered in the clinic and the subject will be observed for at least 1 hour after dosing. For subjects entering the Open Label Extension, the first dose given at Week 24 will be administered in the clinic and the subject will be observed for at least 1 hour after dosing. All other doses will be administered by the subject or the subject's caregiver at home 2×/week, but no dose should be administered on study visit days (see [Section 12.3](#)).

^t Corticosteroid taper will follow the specified algorithm. Corticosteroid tapering at Visit 8 is done for patients entering open label extension only. Reasons for determining worsening will be captured in the eCRF (FVC, DLCO, imaging, symptoms, other). Justification for any deviations will also be captured in the eCRF.

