8. STUDY DESIGN

8.1. Description

This is a multicenter, randomized, double-blind, placebo-controlled exploratory study evaluating the efficacy and safety of Acthar Gel in the treatment of pulmonary sarcoidosis.

The study will have 3 phases: Screening (up to 28 days); double blind treatment (24 weeks); and an optional open-label, 24 weeks extension. A follow-up visit will be conducted 4 weeks (\pm 2 days) after the last dose of IMP is administered.

Following signature of the ICF and a screening period of up to 28 days, subjects who meet all eligibility criteria will be randomly assigned to receive either 1 mL (80 U) of Acthar Gel or 1 mL of a matching placebo SC 2 \times /week. Subjects will be assigned to treatment in a 1:1 ratio with up to 50 subjects per arm for a total of approximately 100 subjects.

Dose reduction of 50% may be implemented once during the study, if a subject meets one of the following prespecified safety criteria based on clinical judgment:

- Uncontrolled hypertension (newly developed or worsening of existing hypertension) before/or in conjunction with addition/adjustment of antihypertensive therapy.
- Uncontrolled diabetic signs/symptoms (newly developed or worsening of existing diabetes) before/or in conjunction with addition/adjustment of antihyperglycemic therapy.
- Unacceptable toxicity defined as any AE of at least moderate intensity not adequately controlled by concomitant medication use or other non IMP-related measure

The justification for dose reduction will be captured in the eCRF. Subjects will remain on the 40 U or matching placebo 2 \times /week for the remainder of the study. Subjects who, despite dose reduction, continue to experience any of the above mentioned AEs, (meet a criteria as above) or experience another event will be withdrawn from the study due to AE ([Section 12.3](#)).

Subjects will be followed every 4 weeks (\pm 5 days) for 24 weeks (Visit 2 to Visit 8). During each visit following Visit 2, steroid tapering evaluation will occur based on the corticosteroid tapering algorithm ([Section 7.2.4](#)). A justification for any deviation will be captured in the eCRF.

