- Both the investigator and the subjects will independently be asked if they would choose to continue treatment. The investigator must respond before seeing the subject's response. Subjects may continue to the optional Open-label Extension Phase irrespective of their response (eg, placebo treated) at the discretion of the principal investigator.
- Subjects declining participation or ineligible (at the discretion of the principal investigator) for the Open-label Extension Phase will have end-of-treatment procedures completed (eg, return or study drug and equipment).
- Contact IXRS.

- For subjects entering the Open-Label Extension Period:
 - Remind the subjects to arrive in fasting condition for Visit 9 (drinking water is permitted) and to bring all IMP kits including used and unused vials to each visit in a cooler.
 - Dispense IMP kits and equipment.
 - Administer Acthar Gel under supervision of study staff and observation for at least 1 hour thereafter.
 - Instruct the subject to inject Acthar Gel 80 U (1 mL) 2×/week unless the subject had a single reduction of dose, in which case only 40 U (0.5 mL) 2×/week will be injected for the remainder of the study.
 - Corticosteroid tapering.

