4.3. Reporting Conventions

The following reporting conventions apply generally to tables, listings, and figures:

- All by-visit summaries and analyses will be provided separately for the double-blind treatment phase and the open-label extension phase, unless otherwise specified. Only subjects who continued to the open-label extension phase will be included in the summaries of open-label extension phase based on the open-label safety populations.

- For subjects who continued into the open-label extension phase, the first dose of IMP at the open-label extension phase will be used as the cutoff date. Since the first dose administration date at the open-label extension phase is not collected electronically, and the dosing schedule is twice/week, either the first IMP kits and equipment dispense date or the next date after completion date of double-blind phase, whichever is the later date, has been used as the best estimate of the first dose of IMP in the open label extension phase. The assessments collected before the cutoff date will be summarized in the double-blind treatment phase and the assessments collected on or after the cutoff date will be summarized in the open-label extension phase, unless specified otherwise. Subjects who did not continue into the open-label extension phase will be summarized in the double-blind treatment phase only.
- Summaries for the double-blind treatment phase will be based on the treatments that the subjects actually received at the double-blind treatment phase. Summaries for the open-label extension phase will also be based on the treatment sequences that the subjects actually received during overall study phase, e.g. Acthar/Acthar and Placebo/Acthar.
- Study Day 1 is defined as the date of the first dose of IMP at the double-blind treatment phase. Study days are calculated as the difference between the date of interest and Study Day 1 plus 1 day. For events before Study Day 1, study days will be calculated as the difference in days between Study Day 1 and the date of interest. The day before the date of the first dose at the double-blind treatment phase will be defined as Day -1. This means there will be no study Day 0.

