9.1. Sarcoidosis Treatment Score (STS)

STS is a newly developed composite score that combines the results of PFT, chest imaging, quality of life, and changes in corticosteroid dosing. Individuals may score from - 6 to + 6. Higher scores indicate improvement. Subjects tolerating Acthar Gel (or placebo) will be categorized as Response, Partial Response, and Non Response. STS can be determined by using the assessments categories as presented in table below.

Table 1: Determining the Sarcoidosis Treatment Score

	Parameter	Improved	Unchanged	Deteriorate
Category of Assessment		+1	0	-1
PFT ^a	FVC	$\geq 5\%$	> -5% to < 5%	$\leq -5\%$
	DLCO	$\geq 5\%$	> -5% to < 5%	$\leq -5\%$
Imaging	HRCT	Improved	Unchanged	Worse
Quality of Life	King's Sarcoidosis Questionnaire (General Health)	≥ 4	> -4 to < 4	≤ -4
	Fatigue Assessment Score	≤ -4	> -4 to < 4	≥ 4
	Corticosteroid taper (dosage)	$\geq 50\%$ reduction	< 50% reduction or ≥ 5 mg increase for less than 2 weeks	≥ 5 mg increase for more than 2 weeks

^aAbsolute change of % predicted.

Subject tolerating Acthar (or placebo) will be categorized according the following scoring:

- Response is defined as scores of $\geq 3/6$ points.
- Partial Response is defined as scores of $2/6$ points or stable with corticosteroid reduction (ie, a total score of +1 due to $\geq 50\%$ reduction in corticosteroid dosage).
- Non Response is defined as scores of $\leq 1/6$ points without significant corticosteroid taper (stable or deterioration).

An STS responder is defined as a subject who has an assessed STS category of Response or Partial Response at 24 weeks (Visit 8) during double-blind treatment phase and at 48 weeks (Visit 11) during open-label phase.

The descriptive statistics for developed STS scores, number and percentage of subjects in each STS response category (response, partial response and non response) will be provided at both 24 weeks (Visit 8) and 48 weeks (Visit 11). At 24 weeks (Visit 8) during double-blind treatment phase, the proportions of STS responder (defined as response or partial response) and non-responder, and corresponding odds ratio will be calculated. The 95% confidence interval (CI) of the odds ratio will be calculated as well based on asymptotic method. Pearson's chi-square test (or Fisher's exact test if any expected count is less than 5) will be used to assess the comparability between treatment groups for the STS responder

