9.8. Corticosteroid Tapering

The number and percentage of subjects who have dose adjustment and justifications for dose change will be summarized at each scheduled visit by treatment group and study phase. Descriptive statistics will be provided for doses and doses change from baseline at each scheduled visit. All corticosteroid dose will be converted to prednisone equivalent dose. Additionally, weekly average prednisone or equivalent daily dose (mg/day) will be calculated from prior and concomitant medication data for prednisone collected prior to week 4 (Visit 3) and post week 48 (Visit 11) and corticosteroid use data collected between week 4 (Visit 3) and week 48 (Visit 11). The average weekly daily dose change and percent change from baseline, and change and percent change from baseline of active treatment to week (from week 25 to week 48 in open-label phase only) will be summarized descriptively by weeks from week 1 to week 24 in double-blind phase and from 25 to week 48 in open-label phase. The line plots of mean (+/- standard error) percent change of average weekly daily dose from baseline by weeks will be provided for double-blind treatment phase and overall study phase.

Subjects whose corticosteroid dosage increased for more than 2 weeks will be considered as failing to corticosteroid taper. Pearson's chi-square test (or Fisher's exact test if any expected count is less than 5) will be used to compare the treatment difference between treatment groups for the percentage of subjects who fail corticosteroid taper in double-blind treatment phase only.

Time to failing corticosteroid taper is defined as:

Time to failing corticosteroid taper (day) = date of failing corticosteroid taper - date of first dose + 1.

Time to failing corticosteroid taper will be summarized by descriptive statistics by treatment group for subjects who fail corticosteroid taper.

A listing will be provided for the corticosteroid use by subject and visit.

10. Safety Analysis

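### The Visit 8 steroid taper step is limited to extension entrants yet counted in the double-blind phase, and the SAP does not say whether the Week 24 dose is taken before or after it

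*SAP*

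**What the plan says.** **Who is tapered at Visit 8.** Footnote t to the schedule in Protocol 4.2 states: "Corticosteroid tapering at Visit 8 is done for patients entering open label extension only". The schedule in SAP Appendix 15.3 repeats it. Protocol 11.5 lists tapering only among the steps for extension entrants, in the same list as the first open-label injection ("Administer Acthar Gel under supervision of study staff and observation for at least 1 hour thereafter"). For "Subjects declining participation or ineligible (at the discretion of the principal investigator) for the Open-label Extension Phase", that section provides end-of-treatment procedures and no taper step. Protocol 8.1 carries no such limit: "During each visit following Visit 2, steroid tapering evaluation will occur based on the corticosteroid tapering algorithm".

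**Which phase the record falls in.** SAP 4.3 estimates the first open-label dose date as "either the first IMP kits and equipment dispense date or the next date after completion date of double-blind phase, whichever is the later date" and uses it as the cutoff. Then: "The assessments collected before the cutoff date will be summarized in the double-blind treatment phase".

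**What is reported.**
- SAP 9.8 tabulates dose adjustments and their reasons by visit, arm and phase. It also says: "Descriptive statistics will be provided for doses and doses change from baseline at each scheduled visit". Weekly average doses are reported as double-blind for Weeks 1 to 24 and as open-label for Weeks 25 to 48.
- SAP 9.1 scores the STS steroid item +1 for a reduction of at least 50%. Partial Response includes a subject who is "stable with corticosteroid reduction (ie, a total score of +1 due to" such a reduction. Response and Partial Response together form the responder group, which is tested between arms at Week 24.
- Protocol 7.4 lists the number of participants on each prednisone dose at Weeks 24 and 48 among the primary outcome measures for registration.

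None of these places says whether the Visit 8 dose is the one on arrival or the one newly ordered.

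**The concern.** Extension entry happens after randomisation, by the subject's choice or at the investigator's discretion, and it can differ between arms. A double-blind table that includes a step open only to entrants mixes the effect of treatment with the decision to continue. A reduction ordered at Visit 8 has also had no double-blind follow-up, so it does not show that the lower dose was tolerated.

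For the adjustment table this follows from stated rules. For the Week 24 dose, the STS steroid item and the registry outcome it is an undefined derivation. The STS item matters most, because it feeds a tested comparison in which one point can decide responder status.

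**Working it through.** The plan gives no figure on this point to reproduce. The checks below use its rules; every entry or taper rate is an assumption.

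**1. Date logic (SAP 4.3).** Let V be the Visit 8 date, with kits dispensed on V and double-blind completion dated V. The cutoff is max(V, V + 1) = V + 1. An adjustment dated V precedes it and is double-blind. A new dose starting on V + 1 falls on the cutoff and is open-label. One decision can therefore be split across phases.

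**2. The adjustment count (SAP 9.8).** Let p be the share of an arm entering the extension and q the share of entrants adjusted at Visit 8. Non-entrants have no taper step, so the share of the arm with a Visit 8 adjustment is p × q. With assumed p of 0.9 and 0.7 and the same q = 0.5 in both arms, the table shows 45% against 35%, although entrants were handled alike. With equal p and q the difference is zero.

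**3. Mean dose change, if the post-decision dose is used.** With equal q and step size in both arms, the artefact (Acthar minus placebo) is −step × q × (difference in entry). For entry 20 points higher on Acthar:
- smallest: −2.5 × 0.5 × 0.2 = −0.25 mg/day
- largest: −10 × 1.0 × 0.2 = −2.0 mg/day

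The sign reverses if entry is higher on placebo.

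**4. Can one step cross the 50% line?** The ladder in Protocol 7.2.4 is 40, 30, 20, 10, 7.5, 5, 2.5, 0 mg.

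| Baseline (mg) | Steps to a cut of at least 50% | Path |
|---|---|---|
| 40 | 2 | 30, then 20 (50%) |
| 30 | 2 | 20, then 10 (67%) |
| 20 | 1 | 10 (50%) |
| 10 | 2 | 7.5, then 5 (50%) |
| 7.5 | 2 | 5, then 2.5 (67%) |
| 5 | 1 | 2.5 (50%) |

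Visit 8 can be the crossing step, but evaluations at Visits 3 to 7 come first. At one ladder step per visit, only a subject at most one net step down after those five evaluations can first cross at Visit 8. If x is the share of entrants who do, the component rate shifts by x × (difference in entry): 0.10 × 0.20 = 2 points, or 0.20 × 0.20 = 4 points.

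**5. Reach into the STS.** The other five items, each −1, 0 or +1, give 3^5 = 243 patterns: 51 sum to 0, 45 to +1 and 30 to +2. Moving the steroid item from 0 to +1 changes pooled responder status at sums 0 and +1 (51 + 45 = 96 patterns), or in 45 if the cases resting on the +1 clause are left out. It changes full Response status at sum +2 (30 patterns). These are counts of equally weighted patterns, not probabilities. With 55 randomised, or 27.5 per arm, one changed subject moves an arm's rate by 1/27.5 = 3.6 points.

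**6. Weekly average.** Taking Week w as Days 7(w − 1) + 1 to 7w, Week 24 is Days 162 to 168. Visit 8 is nominally Day 169, with a window of Days 164 to 174. On Day 169 or later, no day of Week 24 carries the new dose. On Day 164, 5 of 7 days do (same-day start) or 4 of 7 (next-day start). A next-day step from 20 to 10 mg then gives (3 × 20 + 4 × 10)/7 = 14.3 mg instead of 20.

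**The case against.** A reader might infer that the Week 24 steroid results, including the tested STS responder rate, already depend on extension entry. The documents do not support that. Neither SAP 9.1 nor 9.8 says that the post-decision dose is scored, and a dose recorded on arrival carries no effect of the Visit 8 step. In Protocol 11.5 the taper item comes last in the extension list, after dispensing and the first open-label injection, so it can be read as an extension procedure. This stands: for the dose, the STS item and the registry outcome, the fault is an undefined choice.

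Other limits also stand:
- The by-visit dose summary is descriptive and untested, in a study labelled exploratory.
- Taper failure needs an increase lasting more than two weeks, so a reduction ordered at Visit 8 cannot create one.
- The five earlier evaluations make a first crossing at Visit 8 less likely, and its frequency is unknown.
- The 96 of 243 count must not be read as 40% of subjects.

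One could add that the SAP 4.3 cutoff would remove post-Visit 8 days from the double-blind weekly average. That is less secure: the cutoff applies unless the SAP specifies otherwise, and SAP 9.8 sets its own split at Week 24.

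None of this reaches the adjustment table. There the footnote, the cutoff and the by-phase count together produce the dependence.

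**Conclusion.** The point holds in two parts. First, the double-blind count of Visit 8 dose adjustments depends on extension entry and not only on treatment. This rests on stated rules and one assumption, that double-blind completion is dated at Visit 8. Second, the SAP does not define the Week 24 dose relative to the Visit 8 decision. If the later dose is used, the dose summaries, the STS steroid item and the registry prednisone outcome share the dependence. The Week 24 weekly average can be affected when Visit 8 falls before Day 169.

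The size and direction of any between-arm effect are unknown, because the documents give no entry or Visit 8 taper rates by arm. If both rates are equal by arm, the effect is zero. The figures of 2 to 4 points and 0.25 to 2.0 mg/day show scale under assumed rates and do not estimate a bias.

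**What to change.** In SAP 9.1 and 9.8:
- Define the Week 24 dose as the prednisone-equivalent daily dose in force before the Visit 8 taper decision. Use it for the by-visit summaries, the STS steroid item and the registry outcome.
- Assign any dose change ordered at Visit 8 to the open-label phase in all tables and weekly averages, whatever its recorded date.
- Use the same pre-decision dose as the baseline of active treatment for Placebo/Acthar subjects.

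This removes the dependence on extension entry by construction. Separately, Protocol 8.1 must be reconciled with footnote t and Protocol 11.5 on who has a taper evaluation at Visit 8; this point takes no position on which taper rule is right.

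The cost is one extra derivation rule, applied to dated steroid records already collected, with no change to patient care. The Week 24 steroid-reduction rate may be slightly lower if post-decision doses would otherwise have been used.
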